Characteristics of the Study Population

Target population

Study Population: We will use stratified randomized control trial to study association between value markers and objective (complications and cancer recurrence) and subjective (HRQoL, psychological wellbeing) outcomes across intervention groups, over 24 month period. We will recruit newly diagnosed localized PCa patients from UPHS (Hospital of University of Pennsylvania, Presbyterian Medical Center, and Pennsylvania Hospital), Fox Chase Cancer Center and Philadelphia Veterans Administration Medical Center (PVAMC) and randomize them to conjoint analysis intervention (n=360) or control group (n=360). Participants: The sample will consist of 720 newly-diagnosed PCa patients.

Subjects enrolled by Penn Researchers

580

Subjects enrolled by Collaborating Researchers

220

Accrual

Participant availability: UPHS is a large hospital and physician network in greater Philadelphia area. Approximately 1,600 patients with newly diagnosed PCa are evaluated annually: 40-50% undergo surgery (RP or RALP); 30-40% undergo EBRT or BT; 10-20% undergo PT. The urology clinic at the Hospital of the University of Pennsylvania (HUP) treats more than 60% of this group; the rest are treated at Presbyterian Medical Center and Pennsylvania Hospital. Additionally, UPHS has a proton therapy center, providing a unique opportunity to study this new technology. The Philadelphia Veterans Administration Medical Center (PVAMC) cares for 33,000 veterans in Philadelphia area and evaluates ~400 patients with newly diagnosed PCa each year. Fox Chase Cancer Center evaluates ~500 patients with newly diagnosed PCa each year. Together, UPHS, PVAMC, and Fox Chase Cancer Center provide care to socio-demographically diverse population of ~2,500 men newly diagnosed with PCa each year. Thus, our study sample requirement of 720 patients (33% of the available pool) can be fulfilled comfortably, as demonstrated by the successful recruitment for our earlier studies. We estimated sample

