size based on the observed differences in outcomes such as HRQoL (SF-36 and prostate cancer index, PCI) and cost of PCa care across groups. The primary outcome is HRQoL as measured by the SF-36 and PCI sub-scales. A change of 5 to 9 points on PCI is clinically meaningful [272]. Similarly, a difference of 7 points or more on the SF subscales is considered clinically meaningful [272, 275, 301]. Based on our prior research and that of Litwin et al [253, 272], the standard deviations for the PCI and SF-36 scales in samples of men with PCa mostly range from 8 to 14; hence standardized differences (SDs) of $7/14=0.5$ to $7/8=0.87$ will be clinically relevant. The power calculations for Aims 2-4 assume availability of 720 participants who are eligible for randomization into one of the two intervention groups. We assume a conservative intra-class correlation of 0.3 and 4 follow-up measures per subject. The sample size is adjusted to accommodate a 10% missing or dropout rate by 24 months based on rates over a similar period of time in previous studies [272, 275, 301]. We assume 80% power and two-sided level of significance of $\alpha = 0.05$. We have 80% power to detect a 1.2 point difference in PCI or SF-36 sub-scale. Within treatment type, the sample size is reduced to 60 per intervention arm. We have 80% power to detect a 3.0 point difference in sub-scale with 60 patients in each arm. Thus, we will have adequate power to detect differences between treatment groups [302]. Power for identifying utility based profiles and outcomes: We analyzed the levels of power for differences in outcomes between profiles defined by latent classes of attributes-specific utilities with a conservative allocation of subjects to each profile (25 in one vs. 10 in other profile) and less conservative allocation (35 in one profile vs. 35 in other profile) using a logistic model based comparison for a binary outcome (e.g. recovery of baseline HRQoL) with a 2-sided alpha of .0125 (Holms adjustment profiles). In the first allocation, the group difference of 0.56 yields 80% power; for the second allocation an effect size of 0.42 corresponds to power of 90. Thus, with our anticipated effect size of 0.51, we will have adequate power with $n=60$ in each group. (Adjusting for patient characteristics may reduce the effect sizes of the differences between profiles.)

Key inclusion criteria

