After obtaining informed consent, baseline data will be obtained in person prior to the initiation of treatment. Participants will meet with the research assistant to complete the computer-based conjoint analysis tasks. Patient identifiers will be removed to maintain data confidentiality. Only the PI will have access to the master files. For conjoint analysis, each participant will be asked to express his preference for attributes and attribute levels for active surveillance and five active treatments for clinically localized PCa (RP, RALP, EBRT, PT, BT) based on choice sets presented. The choices will vary based on the differing attributes of various treatments ascertained in prior work and focus groups. After pilot testing and refining the conjoint task in Phase 1, final attributes and levels will be used. Trade-offs among treatment features will be calculated in patient-specific utilities or part-worths associated with the attribute levels in the study. For other outcomes, participants will receive the following surveys via mail within 1-2 weeks after enrollment and prior to treatment initiation: SF-36, EPIC, AUA-SI, regret scale, CES-D, MAX-PC, SWD, PSQ-18, CPS, DCS and trust scale. Demographics, health and family history, clinical covariates and cancer progression data will be collected at 3, 6, 12 and 24 month follow-up. Histological tumor grade Gleason score and PSA and annual Elixhauser comorbidity score [257-258] will be obtained from the Pennsylvania Integrated Clinical and Research Database (PICARD), a UPHS, Fox-Chase Cancer Center electronic database, and PVAMC administrative and patient HER database. Retention and survey administration: During enrollment, importance of active participation will be emphasized. All participants will complete self-administered surveys at baseline within 1-2 weeks after enrollment (prior to treatment initiation) and again 3,6,12 and 24 months post-enrollment (see Appendix for copies of instruments, consent and medical chart review form). Non-respondents will be contacted via telephone after 10 days. In case of non-response due to death, cause of death will be noted and the physician investigators will determine cause of death (PCa or non-PCa related). The PCa conjoint analysis task, DCS, CPS and trust scale will be administered at baseline only, immediately after diagnosis of PCa and before treatment decision. Procedure for Data Sharing and Modification coordination: In Phase-1 on the study, data will be generated from focus group meetings that will take place on Penn campus. Focus group data will not be shared with other sites. This data will be used to generate a conjoint analysis instrument. This conjoint analysis instrument will be administered to participants in the intervention arm at all three sites during the Phase-2 of the study. The paper copies of various instruments that all participants complete will be stored at Penn campus in a secure office. In addition, clinical data obtained through chart abstraction will also be stored at Penn campus in a secure office. All electronic data bases will be pass word protected and only the study personal will have access to this data. Raw data will not be shared with other sites, only results in aggregate format with de-identified information will be made available to other sites. Each site PI will be responsible for addressing modifications. Additionally, the Penn site PI [name] will have overall responsibility of tracking all modifications. In case of a reportable event at a site, the site PI will inform Penn IRB and Penn site PI regarding the reportable events. Additionally, during Phase-1 of the study, we will conduct audio/video recording of focus group meetings.

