patients in decision (measured using CPS) using multi-nominal regression model to adjust for observed covariates. Then we will examine if these associations vary across intervention and usual care control groups. We then will repeat the model with other independent variables (decision conflict and trust). Next, we will test the association denoted by path c (direct effect of DCS, CPS, and trust on outcomes). For continuous outcomes (HRQoL, AUA-SI, MAX-PC, CES-D, SWD, and PSQ-18), we will compute area under the curve (AUC) for each measure for each patient. We will analyze AUC summaries with univariate linear models. In our main analysis we will analyze the series of functional status measures using linear mixed models that predict the outcome from time, independent variables and their interaction. We will repeat the analyses described for path c, this time by including treatment received in the models. We will test if the observed effects of DCS, CPS or trust on outcomes will be weaker after controlling for treatment. These analyses will be performed within and between groups (intervention and usual care controls). Specific Aim 3: Hypothesis: Prostate cancer patients in the intervention group undergoing conjoint analysis-value clarification exhibit improved treatment choice, satisfaction with decision, lower regrets, and improved objective and subjective outcomes. Analysis for Specific Aim 3 uses intent-to-treat approach: all randomized participants will be included regardless of whether they drop out of the intervention or study. Analysis will involve comparison of the primary outcomes between intervention and usual care control groups. Improved treatment choice is operationalized as the likelihood of low-risk PCa patients receiving active surveillance than active treatment, and will be compared between intervention and usual care control group. To allow for different trajectories of the outcome measures and to afford flexibility in making contrasts within participants over time and across participants, while simultaneously controlling for potential confounders, we propose the participant-specific or mixed effects linear model, in which the mean outcome depends on fixed covariates and random effects. The primary fixed effects will be indicators for intervention group and hospital. We will also stratify the analysis by type of treatment. The random effects represent the unobserved factors that lead to variation of the individual participants outcome. Random intercepts for each participant permit modeling of natural variation across participants at baseline. In addition, random slopes or random effects for the trajectory of each participant over time, allow for variation of each participant about a mean, overall trajectory across all participants. Although less robust to model misspecification, the mixed effects paradigm offers special flexibility in longitudinal data when exposures vary over time and when dropout and missed visits lead to unbalanced groups. The target of inference is the participant-specific response to treatment over time. At each time point of interest, we will estimate from the fitted model the difference from baseline in outcome for the treatment and control groups and test the difference between these differences. Both univariate and multivariate results will be reported in terms of Wald test, point estimates, and 95% confidence intervals. Specific Aim 4: Hypothesis 4: Prostate cancer patients whose treatment is more concordant with their values markers will experience improved subjective and objective outcomes. This specific aim s for intervention group only. We will analyze the association of the concordance between stated individual preferences and actual treatment received with objective (PCa recurrence and complications), subjective (HRQoL, psychological wellbeing, SWD, and satisfaction with care) outcomes, across treatment groups, adjusting for covariates. Association between the value markers (profiles) and measures of outcomes and personal and clinical characteristics: The value markers will be studied for their relationship with socio-demographic and clinical characteristics. We will also assess the association of value markers with outcomes. We will perform logistic regression with outcomes as the dependent variable and dummy variables for the utility-based profiles obtained earlier as independent variables. We will perform this evaluation with and without adjusting for patient attributes in the logistic model. For each case (adjusting and not adjusting for patient attributes), the evaluation of association between these profiles and outcomes will be based on a likelihood ratio test of the set of odds ratios corresponding to the dummy variables of the profiles. Additionally, we will perform a sequence of pair wise tests of comparisons of the profiles in terms of the proportion of type of treatment received based on the Holms multiple comparisons approach. This procedure is hierarchical in that it will identify the utility-based profile at the start of the process before making other comparisons, thus protecting the Type I error from additional comparisons. Specifically, Holms approach tests each pair-wise comparison in ascending order of p-values. Successively larger p-values have less rigorous alpha. The sequential Holm tests terminate after the first non-significant comparison so no subsequent comparison is significance. Concordance and its assessment: Understanding and respect for the patients preference and values is the main aspect of concordance [69, 73]. Thus a first step in concordance involves the physician extracting and understanding the patients view, followed by an agreement between the physician and patient regarding a management plan that integrates their views. There exist many definitions of concordance. For the purpose of this study, we operationalized concordance as agreement between a patients value markers and the attributes (or characteristics) of the treatment that

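### The 720-man power statement is applied to Aim 4, but the concordance hypothesis uses only the intervention arm and has no power figure of its own

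*Combined protocol and SAP*

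**What the plan says.** The sample-size paragraph (Characteristics of the Study Population, Accrual) gives a single statement for three aims: "The power calculations for Aims 2-4 assume availability of 720 participants who are eligible for randomization into one of the two intervention groups". From it the plan states 80% power for 1.2 points on a PCI or SF-36 sub-scale, and for 3.0 points within a treatment type with 60 men in each arm. The same paragraph calls 5 to 9 points (PCI) and 7 points or more (SF-36) clinically meaningful.

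The Analysis Plan says of Specific Aim 4: "This specific aim s for intervention group only". Study Procedures gives the likely reason: "This conjoint analysis instrument will be administered to participants in the intervention arm at all three sites during the Phase-2 of the study". Values markers, and so concordance between markers and treatment, are needed for this aim, and the intervention arm has 360 men.

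Under Aim 4, men are grouped as concordant at 75% agreement or more, and degree of concordance is also used as a predictor. For the subjective outcomes, the primary comparisons are baseline with 6 and with 24 months. No expected concordant share is given.

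A second power paragraph under Accrual deals with latent utility profiles: a binary outcome, 25 versus 10 or 35 versus 35 men, and alpha 0.0125.

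**The concern.** The power statement describes a 1:1 randomised contrast of 360 with 360. Aim 4 differs in two ways. It has half the men, and it divides them by a characteristic that nobody controls and that may split them unevenly. Both changes widen the standard error. The profile calculation does not fill the gap, because membership of a utility profile is not agreement between that profile and the treatment received.

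Concordance is one of the two clauses of the study hypothesis in the Abstract. If Aim 4 gave a null result, a reader relying on the sample-size text would take it that a difference of 1.2 points had been sought with 80% power. That would overstate how much the null result excludes.

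**Working it through.** **Inputs from the sample-size paragraph.** Two-sided alpha 0.05 and 80% power, so the multiplier is 1.9600 + 0.8416 = 2.8016. On repeated measures: "We assume a conservative intra-class correlation of 0.3 and 4 follow-up measures per subject". Planned loss is 10%, which takes 360 to 324 and 60 to 54. For the SD: "the standard deviations for the PCI and SF-36 scales in samples of men with PCa mostly range from 8 to 14".

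**Step 1: reproduce the plan's figures.** The variance of a mean of four equally correlated visits is SD² × (1 + 3 × 0.3)/4 = 0.475 × SD². At SD 8 this is 64 × 0.475 = 30.4.

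- 324 per arm: 2.8016 × √(2 × 30.4/324) = 1.21 points (stated 1.2). Power at exactly 1.2 is 79%.
- 54 per arm: 2.8016 × √(2 × 30.4/54) = 2.97 points (stated 3.0).

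Other variants fail on at least one figure. Without dropout, 60 per arm gives 2.82. At SD 14, 324 per arm gives 2.12. A single visit at SD 8 gives 1.76. The stated figures therefore rest on SD 8, the low end of the plan's range, with four visits and 10% loss.

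**Step 2: the same basis on the Aim 4 sample.** Let f be the concordant share of 324 men. It is not in the documents, so 50%, 25% and 10% are assumptions that show a range.

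SE = √(0.475 × SD² × [1/(324f) + 1/(324(1 − f))]); detectable difference = 2.8016 × SE; power at 1.2 = Φ(1.2/SE − 1.96).

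| Concordant share | Group sizes | SE, SD 8 | Detectable, SD 8 | Power at 1.2, SD 8 | Detectable, SD 14 |
|---|---|---|---|---|---|
| 50% | 162 / 162 | 0.613 | 1.72 | 50% | 3.00 |
| 25% | 81 / 243 | 0.707 | 1.98 | 40% | 3.47 |
| 10% | 32.4 / 291.6 | 1.021 | 2.86 | 22% | 5.01 |

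An equal split gives the smallest SE, so 50% is the ceiling after the plan's dropout; with all 360 men it would be 54%. Holding SD at 8 isolates the effect of sample and split. At SD 14 the full 720-man design itself has only 35% power for 1.2 points.

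**Step 3: compare with the plan's meaningful differences.** On this four-visit basis, pooled Aim 4 power at 5 points is above 99% at SD 8 for all three splits. At SD 14 it is 99.7%, 98% and 80%. At 7 points it is at least 97% throughout.

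**Step 4: sensitivity to the time-point basis.** The planned primary comparisons for subjective outcomes use baseline with one later visit, not a four-visit mean. Taking 0.3 as the correlation with baseline too (an assumption), a change score has variance 2 × SD² × (1 − 0.3) = 1.4 × SD².

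- SD 8 (variance 89.6): detectable differences of 2.9, 3.4 and 4.9 points for the three shares.
- SD 14 (variance 274.4): 5.2, 6.0 and 8.6 points, with power at 5 points of 78%, 65% and 37%, before any multiplicity correction.

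**The case against.** The strongest reply is that 1.2 points is a detectable difference, not a target. The plan's meaningful differences are several times larger, and step 3 shows that pooled Aim 4 keeps about 80% power or more for them on the four-visit basis. This stands. A reader might infer from power of 50% or 22% at 1.2 points that the concordance aim is underpowered; the documents do not support that for pooled men.

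Three further replies stand in part.

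- Part of Aim 4, the association of profiles with outcomes, has its own calculation. The gap is therefore concordance, not the whole aim.
- The two-group arithmetic covers only one of the planned analyses. Degree of concordance is also used in regression and mixed models, and the time points differ from a four-visit mean. The figures show the scale of the mismatch and do not replace a proper calculation.
- A reader might also set a within-treatment concordance contrast against the stated 3.0 points. That comparison does not hold: the 3.0 is a between-arm figure with 60 men in each arm and was never a claim about concordance.

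It could also be said that Subject recruitment expects conjoint tasks from 800 men, and that Procedures speaks of each participant expressing preferences, so markers might exist in both arms. The restriction in Specific Aim 4 is explicit, however, and the data-sharing text in Procedures agrees with it. The looser wording does not enlarge the Aim 4 sample.

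**Conclusion.** The point holds as an error of scope in the power statement. The 1.2 and 3.0 points are correctly computed for a randomised between-arm contrast at SD 8. They do not apply to the concordance hypothesis, for which the plan gives no power figure. With everything else held as the plan has it, the best case for Aim 4 is 1.7 points instead of 1.2, a factor of √2 from halving the men. Unequal assumed shares take it to 2.0 or 2.9 points at SD 8. The corresponding range at SD 14 is 3.0 to 5.0.

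The equal-split figures need only the plan's inputs and the equal-correlation model that reproduces 1.2. The others rest on concordant shares that the plan does not supply. To rounding, all lie at or below the lowest meaningful difference of 5 points, so the error is in the stated precision. Step 4 shows that this margin depends on the time-point basis and can disappear at SD 14. That is a reason to state the basis, not evidence that the aim fails, since it adds an assumption about the correlation with baseline. The point should be fixed, but it does not threaten the design.

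**What to change.** Limit the 720-based 1.2-point figure and the 60-per-arm 3.0-point figure to the randomised between-arm comparison: Aim 3, and any part of Aim 2 that contrasts the arms. Rewording the sentence to cover Aims 2 and 3 in full would not be enough. Most of Aim 2 concerns associations of decision conflict, trust and role preference with outcomes, and these are not 1:1 randomised contrasts.

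Add an Aim 4 concordance line on 360 intervention-arm men (324 after 10% loss). It should state the SD, the assumed concordant shares (for example 50%, 25% and 10%), and the time-point basis actually planned, baseline versus 6 and 24 months. Bring the wording on who completes the conjoint task into line with the Aim 4 restriction.

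The cost is protocol wording and a short calculation. Recruitment, design and analysis stay as they are; the stated precision for Aim 4 becomes less favourable.

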
item scale that assesses eight health domains. This instrument can be self-administered or administered by a trained interviewer, either in person or by telephone. It has been tested extensively for reliability ($r=0.80 - 0.93$) and validity (Cronbachs $=0.92$). Scores on each sub-scale range from 0 to 100, with higher scores indicating better HRQoL [267-271].

D.2.4.3.4 Prostate Cancer HRQoL- Expanded Prostate Cancer Index (EPIC): The EPIC was developed for comprehensive assessment of HRQoL in men with PCa. It is a 50-item expanded edition of the 20-item UCLA Prostate Cancer Index (PCI) and complements other instruments by measuring a broad spectrum of urinary, bowel, sexual and hormonal symptoms. It has good psychometric properties: test-retest reliability and internal consistency are high for EPIC and for most of the subscales [189, 272-273]; construct validity was established using SF-36 as a generic core measure and a cancer-related HRQoL instrument, the Cancer Rehabilitation System-Short Form [189, 272-273]; and is easy to understand and complete [192].

D.2.4.3.5 American Urological Association Symptom Index (AUA-SI): The AUA-SI, a clinically sensible, reliable, valid and responsive index widely used for clinical and research purposes [274], has good internal consistency (Cronbachs $=0.86$), excellent test-retest reliability ($r=0.92$) and sensitivity to change with preoperative scores decreasing from a mean of 17.6 to 7.1 by four weeks after prostatectomy ($p<0.001$).

D.2.4.3.6 Patient Satisfaction Questionnaire (PSQ-18): This 18-item survey [a shorter version of the original Patients Satisfaction Questionnaire [275], assesses global satisfaction with medical care and satisfaction with six aspects of care: technical quality; interpersonal manner; communication; financial aspects of care; time spent with doctor; and accessibility of care. It has demonstrated good internal consistency (Cronbachs $=0.86$) and excellent test-retest reliability ($r=0.92$).

D.2.4.3.7. Memorial Anxiety Scale for Prostate Cancer (MAX-PC): The 18-item MAX-PC identifies three aspects of PCa-related anxiety. It has high internal consistency and concurrent and discriminant validity[276].

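### The ICC of 0.3 is called conservative, but neither that label nor the 1.2- and 3.0-point detectable differences fit together for the change-from-baseline test planned under Aim 3

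*Combined protocol and SAP*

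**What the plan says.** The power statement is under Characteristics of the Study Population, Accrual. It works at two-sided 5% significance and 80% power, and says "We assume a conservative intra-class correlation of 0.3 and 4 follow-up measures per subject". On spread, it says that "the standard deviations for the PCI and SF-36 scales in samples of men with PCa mostly range from 8 to 14". On attrition: "The sample size is adjusted to accommodate a 10% missing or dropout rate by 24 months". The results are "We have 80% power to detect a 1.2 point difference in PCI or SF-36 sub-scale" with 360 per arm, and "We have 80% power to detect a 3.0 point difference in sub-scale with 60 patients in each arm". From the second figure it concludes that power for comparisons between treatment groups is adequate. It sets clinically meaningful differences at 5 to 9 points (PCI) and 7 points or more (SF-36).

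The text does not give the variance formula, the SD used, the contrast that is powered, a source for the ICC, or results at any other ICC.

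The Analysis Plan, Specific Aim 3, describes a mixed model. At each time point it estimates each arm's difference from baseline and tests the difference between those differences. It also stratifies the analysis by type of treatment.

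**The concern.** Whether a low ICC is cautious depends on the contrast. For a between-arm difference in the mean of several follow-up visits, higher within-man correlation means that repeat visits add less information, so a low ICC flatters the power. For a change from baseline, higher correlation removes more between-man variation, so a low ICC is the cautious choice. The plan uses the label without saying which contrast it powered, and the contrast that most simply returns its figures is not the one Aim 3 tests.

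At stake is what the funder and the DSMB are told. They read that the power rests on a cautious input and that small differences are detectable, including within treatment type, where the arms have only 60 men each.

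**Working it through.** **Inputs.** Two-sided alpha 0.05 and 80% power (1.960 + 0.842 = 2.802); ICC 0.3; four follow-up measures; SD 8 to 14; 360 and 60 per arm; 10% dropout, so 360 × 0.9 = 324 and 60 × 0.9 = 54 (all from Accrual). Assumptions made here: equal correlation between all visits, including baseline, and visits treated separately in time. Detectable difference = 2.802 × SD × √(2/n × V), where V depends on the contrast.

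**Step 1: reproduce the plan's figures.** For the unadjusted mean of four visits, V = (1 + 3 × ICC)/4 = 0.475 at ICC 0.3. With SD 8:
- 324 per arm: 2.802 × 8 × √(2/324 × 0.475) = 1.21 points; power for 1.2 points is 79%.
- 54 per arm: 2.802 × 8 × √(2/54 × 0.475) = 2.97 points; power for 3.0 points is 81%.

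Both stated figures are recovered from printed inputs.

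**Step 2: vary the ICC in that model (SD 8).** V rises with the ICC.

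| ICC | V | Detectable, 324 per arm | Power for 1.2 | Detectable, 54 per arm | Power for 3.0 |
|---|---|---|---|---|---|
| 0.3 | 0.475 | 1.21 | 79% | 2.97 | 81% |
| 0.5 | 0.625 | 1.39 | 68% | 3.41 | 69% |
| 0.8 | 0.850 | 1.62 | 54% | 3.98 | 56% |

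The values 0.5 and 0.8 are assumptions.

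**Step 3: the Aim 3 contrast.** For a single-visit change from baseline, V = 2(1 − ICC) = 1.4 at ICC 0.3. For the four-visit mean minus baseline, V = 1.25(1 − ICC) = 0.875. Detectable differences at 324 / 54 per arm:

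| Contrast | ICC | SD 8 | SD 14 |
|---|---|---|---|
| Single-visit change | 0.3 | 2.08 / 5.10 | 3.65 / 8.93 |
| Single-visit change | 0.8 | 1.11 / 2.73 | 1.95 / 4.77 |
| Four-visit mean minus baseline | 0.3 | 1.65 / 4.03 | 2.88 / 7.06 |
| Four-visit mean minus baseline | 0.8 | 0.88 / 2.16 | 1.54 / 3.77 |

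Here a higher ICC helps. At the plan's own ICC of 0.3, however, neither form gives 1.2 and 3.0 at any SD from 8 to 14. At SD 8, power for 1.2 points is 37% (single visit) or 53% (mean minus baseline). Ignoring dropout does not close the gap: with 360 and 60 per arm at SD 8, the single-visit change gives 1.98 and 4.84, and the mean minus baseline 1.56 and 3.83.

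**Step 4: power at the plan's meaningful differences.**
- Overall, least favourable case above (single-visit change, SD 14, ICC 0.3): standard error 14 × √(2/324 × 1.4) = 1.30; 5/1.30 = 3.84; power about 97% for 5 points.
- Within treatment type, same case: standard error 14 × √(2/54 × 1.4) = 3.19; power about 35% for 5 points and 59% for 7 points. At ICC 0.8 these become about 84% and 98%.
- Within treatment type, unadjusted four-visit mean at SD 14: power for 5 points is 77% at ICC 0.3 and 52% at ICC 0.8; for 7 points, 97% and 80%.

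**The case against.** The strongest reply is that the plan never states the four-visit mean, and other models also return its figures.
- **Four-visit mean adjusted for baseline:** V = (1 + 3 × ICC)/4 − ICC². This gives 1.23 and 3.01 at SD 9.0 with 324 and 54 per arm, and 1.22 and 2.98 at SD 9.4 with 360 and 60. V peaks at ICC 0.375, so 0.3 is close to the worst case, and at SD 9 power for 1.2 points never falls below about 77%.
- **Purely within-man variance:** V = (1 − ICC)/4 gives 1.22 and 3.00 at SD 14 with 360 and 60 per arm. A low ICC is again cautious, although this form suits a slope-type contrast better than a difference in means and leaves out the dropout.

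In addition, Aim 3 uses baseline, so the label points the right way for the planned test. The documents give no longitudinal ICC: the SF-36 reliability of 0.80 to 0.93 is a property of the instrument, not a correlation over 24 months that span treatment. And 1.2 and 3.0 points are detectable differences, not targets.

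All of this stands, and it rules out two readings that a reader might infer. One is that 0.3 is an optimistic input whatever SD was used, so that true power is 54% to 68%; that needs both an unstated model and an assumed ICC. The other is that the trial is underpowered overall; Step 4 shows that it is not.

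The reply does not rescue the text. Accrual mentions no baseline adjustment, and none of the models that fit is the visit-by-visit change that Aim 3 tests.

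**Conclusion.** The point holds in limited form. The label and the two stated figures cannot both be carried over to the planned test. If the unadjusted four-visit mean was powered, the label is unsupported, because any ICC above 0.3 lowers the stated power. If the Aim 3 contrast is the one that matters, the label is right in direction, but at ICC 0.3 the detectable differences are about 2.1 to 3.6 points overall and 5.1 to 8.9 within treatment type for a single-visit change, or 1.65 to 2.9 and 4.0 to 7.1 for the four-visit mean minus baseline. With a high ICC and an SD near 8 the change contrast would reach the stated figures, but the plan does not assume that.

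The practical consequence is confined to the comparisons within treatment type. At ICC 0.3 the single-visit detectable difference there passes 7 points once the SD exceeds about 11 (8 × 7/5.10), so the statement of adequate power is doubtful at the upper SDs. These results rest on equal correlation between visits. The random slopes in Aim 3, or a straight-line time trend, would change the variances. Which model the authors used cannot be settled from the documents.

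**What to change.** In the Accrual text:
- Name the contrast powered, the SD used and the variance formula, and give the basis for the ICC.
- Restate the detectable differences for the Aim 3 contrast, overall and within treatment type, over SD 8 to 14 and ICC 0.3 to 0.8.
- Keep the word conservative only if the change-from-baseline contrast is the one powered; delete it if the four-visit mean is kept.
- Qualify the statement of adequate power within treatment type by giving the SD and ICC at which it holds for 5 and 7 points.

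The cost is a short table and a few sentences. No extra patients and no design change are needed. The only downside is that the stated figures become less favourable.
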